46 end of the procedure the mucosal opening is closed with clips. In our centre we have
47 now treated more than 10 patients successfully with POEM and we were able to confirm
48 the positive findings in symptom improvement and lower oesophageal sphincter
49 pressure reduction reported by the German and Japanese pioneers of the technique.^{8,9}

50 **2 HYPOTHESIS**

51 We hypothesize that POEM has a higher long-term efficacy than PD in treatment of
52 therapy-naive patients with idiopathic achalasia.

53

54 **3 AIM**

55 To compare the efficacy of POEM to the efficacy of PD as the initial treatment of
56 symptomatic idiopathic achalasia.

57

58 **4 STUDY DESIGN**

59 This is a multi-centre randomised clinical trial in which a new treatment (POEM) will be
60 compared to the gold standard (PD). The primary endpoint will be measured at two
61 years after treatment and follow up will be extended up to five years.

62

63 **5 PRIMARY OUTCOME**

- 64 • Treatment success, defined as:
- 65 ○ An Eckardt score of 3 or less
 - 66 ○ The absence of the need for endoscopic or surgical retreatment in the
67 period between the first treatment session (first and optional second
68 dilation within first 3 months) and the endpoint
 - 69 ○ The absence of severe complications associated with treatment.

70

71 **6 SECONDARY OUTCOMES**

- 72 • Quality of life and achalasia-specific quality of life
- 73 • Stasis in the oesophagus, measured with a timed barium oesophagogram
- 74 • Presence of reflux symptoms, reflux oesophagitis and excessive oesophageal
75 acid exposure
- 76 • Lower oesophageal sphincter pressure and integrative relaxation pressure
77 (IRP4), as measured with high-resolution manometry
- 78 • Complications of the treatment, defined as any unwanted events that arise
79 following treatment and/or that are secondary to the treatment. Complications are
80 classified as “severe” when these result in admission > 24 hours or prolongation
81 of an already planned admission of >24 hours, admission to a medium or

82 intensive care unit, additional endoscopic procedures, or blood transfusion or
83 death. Other complications are classified as “mild”.

- 84 • The need for endoscopic or surgical retreatment after the initial treatment session

85

86 **7 POPULATION**

87 **7.1** *Subjects*

88 Adult patients with symptomatic idiopathic achalasia that have not undergone
89 endoscopic or surgical treatment for achalasia before.

90

91 **7.2** *Inclusion criteria:*

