136 have been performed within the last 6 months and of high quality (at the discretion of the
137 investigator) it is not required to repeat this. Questionnaires regarding symptoms and
138 quality of life (see 8.4) are filled in by the patients.

139

140 **General follow up**

141 Patients that are randomised to endoscopic balloon dilation will be asked to fill in an
142 Eckardt score three weeks after the dilation. If this score is still more than 3, they will be
143 scheduled to undergo a second pneumatic dilation, but now using a 35 mm balloon
144 (figure 1). Manometry is performed if the Eckardt score is 3 or less. If the manometry

145 shows an IRP of more than 10, patients will also undergo a second pneumatic dilation
 146 (with a 35 mm balloon).
 147 Manometry and timed barium oesophagography are performed and questionnaires are
 148 filled in all patients 3 months after treatment and at 1, 2 and 5 years after treatment.
 149 Twenty-four hour pH-impedance monitoring is performed one year after treatment to
 150 evaluate oesophageal acid exposure. Upper endoscopy is performed at 1, 2 and 5 years
 151 after treatment.
 152
 153
 154

155
 156 *Figure 1 Treatment algorithm used in this study*
 157

158
 159
 160
 161
 162
 163

	Baseline	3 weeks*	3 months	1 year	2 years	5 years
Blood count, chemistry, clotting	X					
Questionnaires	X	Eckardt*	X	X	X	X
Timed barium oesophagography	X		X	X	X	X
Manometry	X	If Eckardt >3*	X	X	X	X
Upper endoscopy	X			X	X	X
pH-impedance monitoring				X		

164

165

Table 1 Schedule of baseline and follow-up examinations; * only for patients randomised to balloon dilation

166

167

168 **8.2 Pneumodilation (PD)**

169 In this study pneumodilation will only be performed by experienced endoscopists, that
170 have performed over 20 pneumodilation procedures. Patients are asked to use clear
171 fluids only starting 24 hours before the procedure and nil per mouth starting 8 hours
172 before the procedure. Under fluoroscopic guidance a Rigiflex balloon (Boston Scientific)
173 is positioned at the esophagogastric junction and dilated at a pressure of 5 PSI, followed
174 by dilation with 8 PSI for one minute (Figure 2).^{8,10} The initial pneumatic dilation is
175 performed using a 30-mm balloon. Three weeks later the symptoms of patients are
176 evaluated using the Eckardt score. If the Eckardt score is still higher than 3, a
177 subsequent dilation with a 35-mm balloon is scheduled. If the Eckardt score is less than

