178 3 a subsequent high-resolution manometry is scheduled. If this shows an integrative
179 relaxation pressure (IRP4) of more than 10 mmHg, a subsequent dilation with a 35-mm
180 balloon is scheduled as well. In total, patients will thus undergo one or two pneumatic
181 dilations in the first 6 weeks. A second dilation within this 6 week period is not
182 considered a failure but considered part of the regular treatment. PPI are taken orally in
183 a single daily dose for two weeks after each dilation.

[figure not shown]

Figure 2 Schematic outline of a pneumatic balloon dilation

[figure not shown]
184
185
186
187

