APPENDIX A

Calculation of the Eckardt score

Each patient has to answer four questions that concern different symptoms. Per symptom they have to mark the degree of severity of the specific symptom. Each symptom is scored from 0-3 and the Eckardt score is the sum of symptom scores. The minimum score is 0 and the maximum score is 12. A high Eckardt score indicates severe complaints due to achalasia.

Score	0	1	2	3
Questions/Symptoms				
Dysphagia (difficulty or pain during swallowing)	No (0)	Occasionally (1)	Daily (2)	At each meal (3)
Regurgitation (food is coming back in to the mouth)	No (0)	Occasionally (1)	Daily (2)	At each meal (3)
Chest pain	No (0)	Occasionally (1)	Daily (2)	At each meal (3)
Weight loss	0 kg (0)	0-5 Kg (1)	5-10 kg (2)	> 10 kg (3)

584
585
586
587
588
589
590
591
592
593
594
595
596
597
598
599
600
601

602 **16 ADDENDUM**

603

604 **Treatment failure in the POEMA Trial**

605

606 **Description of treatment failure**

607 Study subjects are considered treatment failures in case the **Eckardt score is > 3**
608 **within the first 2 years of follow-up, retreatment is indicated or a treatment related**
609 **SAE occurred** after the initial treatment. This means that the study subjects did not
610 achieve the primary endpoint, 2 years after the initial treatment, due to recurrent
611 symptoms.

612

613 The vast majority of failed study subjects will need retreatment and the indication for
614 retreatment should be based on the symptoms of the subject (Eckardt > 3) in
615 combination with:

- 616 - Considerable LES pressure or IRP (> 10mmHg) on HRM.
- 617 - Significant stasis on timed barium esophagogram.
- 618 - Clinical judgement and expert opinion of the treating physician.

619

620 **Treatment of treatment failures** (*see algorithm below*)

621 POEM procedure

622 Study subjects failed on POEM will be retreated with pneumodilation. The first step is to
623 perform a pneumodilation with a 30 mm rigiflex balloon in a single session. The effect of
624 the pneumodilation should be evaluated by the Eckardt score. In case the Eckardt is >3
625 a new pneumodilation should be scheduled with one step larger balloon size. There is
626 no limit to the number of pneumodilations that can be performed after a failed POEM.

627

628

629 Pneumodilation with 30 and 35 mm balloon

630 Study subjects failed on the initial pneumodilations (30 and 35 mm rigiflex balloon) within

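### Table 1 reverses the Eckardt condition for the 3-week manometry in the pneumodilation arm, and section 8.2 gives no rule for a score of exactly 3

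*Protocol*

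**What the plan says.** The Protocol describes the 3-week decision in the PD arm in three places.

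- **Section 8.1, General follow up.** After the first (30 mm) dilation the patient completes an Eckardt score at three weeks. "If this score is still more than 3, they will be" scheduled for a 35 mm dilation. For the others, "Manometry is performed if the Eckardt score is 3 or less", and an IRP above 10 also leads to the 35 mm dilation.
- **Table 1, manometry row, 3-week column.** The cell makes manometry conditional on an Eckardt score above 3. Its asterisk refers to the footnote "only for patients randomised to balloon dilation".
- **Section 8.2, Pneumodilation.** A score above 3 leads to the 35 mm dilation. The next sentence begins "If the Eckardt score is less than" and continues "3 a subsequent high-resolution manometry is scheduled", with IRP4 above 10 mmHg as the trigger for dilation. Patients therefore have one or two "dilations in the first 6 weeks", and the second one is not counted as failure.

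Two other places bear on the consequences. Section 5 places the optional second "dilation within first 3 months) and the endpoint" inside the initial treatment. The addendum says that the indication for "retreatment should be based on the symptoms of the subject (Eckardt > 3) in" combination with manometry, barium findings and clinical judgement.

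**The concern.** The 3-week manometry is a treatment decision point. It is the only stated route by which a PD patient with an Eckardt score of 3 or less receives the second dilation, and that dilation is part of the comparator. The sample size section sets the PD success rate with reference to a two-step dilation strategy.

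A centre that works from Table 1 would do two things wrong:

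1. It would omit the IRP measurement in patients scoring 3 or less, the group in which the result decides treatment.
2. It would pass a transnasal catheter in patients scoring above 3, who are dilated whatever the result.

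In a multi-centre trial, centres reading different parts of the protocol could deliver different PD regimens.

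The gap in section 8.2 is smaller. Read alone, that section sends a patient scoring exactly 3 to neither manometry nor dilation.

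**Working it through.** **Inputs.** The three rules come from sections 8.1 and 8.2 and Table 1. The Eckardt score is the sum of four items scored 0 to 3 (section 8.4 and Appendix A), so it takes whole values from 0 to 12. A score of 3 is attainable, and it is also the upper limit for success in section 5.

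**What each place prescribes at three weeks for a PD patient**

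| Eckardt score | Section 8.1 | Section 8.2 | Table 1 |
|---|---|---|---|
| 0, 1, 2 | manometry; dilate if IRP > 10 | manometry; dilate if IRP4 > 10 | no manometry |
| 3 | manometry; dilate if IRP > 10 | no rule | no manometry |
| 4 to 12 | dilate | dilate | manometry |

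- Table 1 disagrees with section 8.1 at all 13 possible scores (0 to 12).
- Table 1 disagrees with section 8.2 at the 12 scores that section covers (3 + 9 = 12).
- Sections 8.1 and 8.2 differ only at a score of 3.

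The table condition is therefore inverted, not merely worded differently.

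**Can the omitted step be made up later?** The next scheduled manometry is at 3 months, about 13 weeks. That is after the 6-week period in section 8.2 and at the limit of the 3-month period in section 5. No rule links the 3-month result to a second initial dilation. The addendum bases later retreatment on an Eckardt score above 3 together with other findings, so a patient with few symptoms and a raised IRP would not qualify on that basis.

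**Scale.** Enrolment of 130 at 1:1 gives 130 / 2 = 65 PD patients. One PD patient whose 2-year outcome changed would move the PD success rate by 1 / 65 = 1.5 percentage points. The protocol gives neither the share of PD patients scoring 3 or less at three weeks nor the share of those with IRP above 10. The number affected, and hence the total effect, cannot be computed.

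**Sample size.** The plan's figure reproduces and does not depend on this point. With p1 = 0.70, p2 = 0.90, mean 0.80, two-sided alpha 0.05 and 80% power:

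n = [1.96 × √(2 × 0.80 × 0.20) + 0.8416 × √(0.70 × 0.30 + 0.90 × 0.10)]² / 0.20² = (1.1087 + 0.4610)² / 0.04 = 61.6, rounded up to 62 per group.

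Power at 62 per group is 80.3%. Allowing for 5% loss, 124 / 0.95 = 130.5, in line with the stated 130.

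**The case against.** The strongest reply is that the treatment rule is not really in doubt. Section 8.1 states it in full just before the table, and section 8.2 repeats the direction and the trigger. Table 1 lists examinations and contains no dilation rule, so a centre cannot run the PD step from the table alone. Harm requires a centre to follow one cell against two sections of text. This stands, and it is why the effect may be nil. It does not make the cell right: a visit schedule is what staff use to book tests, and this one books the test for the wrong patients.

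Further points:

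- **Score of exactly 3.** Section 8.1 covers it, so the protocol read as a whole has a rule, and section 8.2 is silent rather than contrary. That is fair. The gap is a wording error within section 8.2, secondary to the table.
- **Figure 1.** The treatment algorithm is not shown in the text available, so which version it supports is unknown. If it agrees with the text, the risk is lower.
- **Misread symbol.** The table point rests on one symbol, and an error in reading the PDF cannot be fully excluded. Inequality signs elsewhere read sensibly, however, and the section 8.2 error is in words.
- **Direction of effect.** Omitting a second dilation withholds treatment but also avoids a procedure with about 3% perforation risk (sections 1 and 9.2), and severe complications count as failure. The net direction for PD success is unknown.
- **Later dilation.** Not every delayed second dilation would count as failure, because section 5 allows it within 3 months. This also stands.

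**Conclusion.** The concern holds. Table 1 states the reverse of the 3-week manometry rule in sections 8.1 and 8.2, and section 8.2 leaves out a score of exactly 3. A slip in the table is the likely cause, because both text sections agree on the direction.

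Neither the size nor the direction of any effect on PD success can be derived from the protocol. If all centres followed section 8.1, there is none. Beyond that, the only scale is about 1.5 percentage points per PD patient whose outcome changed, assuming 65 PD patients. The endpoint definition, power and sample size are untouched.

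The point should still be fixed, because it is a contradictory instruction on how the control treatment is delivered. The conclusion assumes that the table symbol was read correctly and makes no assumption about Figure 1.

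**What to change.** 1. In Table 1, manometry row, 3-week column, change the condition to Eckardt ≤ 3 and keep the asterisk for the PD arm.
2. In section 8.2, change the manometry threshold from less than 3 to 3 or less, to match section 8.1.
3. Check that Figure 1 shows the same rule.
4. Notify the centres of the correction.

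The cost is one table cell and one phrase by amendment, a check of one figure and a note to the centres. No extra patients, procedures or data are needed.

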8.3 Per-oral endoscopic myotomy (POEM)

189 In this study POEM will only be performed by experienced endoscopists, that have
190 performed over 10 POEM procedures. Patients are admitted two hours prior to the
191 POEM procedure and are discharged the next day. Patients are asked to use a diet with
192 clear fluids starting 24 hours before the procedure and nil per mouth starting 8 hours
193 before the procedure. On the day of the procedure, antibiotics and double dose PPI
194 (proton pump inhibitor) are administered intravenously. A PPI will be taken orally for two
195 weeks in a single daily dose starting at the day of treatment. POEM is performed under
196 general anesthesia and with endotracheal intubation. The mouth, throat and esophagus
197 are rinsed with saline and chlorhexidine (40–60 ml). POEM procedures are then
198 performed as described by Inoue et al. (figure 3).⁸

199 A forward-viewing upper endoscope (GIF H180J; Olympus, Hamburg, Germany) is used
200 with a transparent distal cap (MH 588; Olympus). Carbon dioxide gas is used for
201 insufflation during the procedures. An endoscopic dissection knife (KD-640L
202 TriangleTipKnife; Olympus) is used to access the submucosa, to create the submucosal
203 tunnel, and also to divide circular muscle fibers over a minimum length of 6 cm in the
204 esophagus, and 2 cm onto the cardia according to the standards of surgical myotomy.
205 An electrogenerator (Erbe Vio 300D; Erbe Elektromedizin, Tübingen, Germany) is used

206 with Endocut Q mode (effect 2) to open the mucosa, and spray coagulation mode (effect
 207 2, 50 watt) to dissect the submucosa and divide the muscle fibers. A coagulating forceps
 208 (FD-410LR Coagrasper; Olympus) is used for hemostasis as needed. Closure of the
 209 mucosal entry site is performed using standard endoscopic clips (HX-110UR EZ Clip
 210 Reusable Rotatable Clip Fixing Device and HX-610-135L Single Use Clips; Olympus).
 211 On the next day postoperative fluoroscopy is performed to rule out a leak at the
 212 esophageal closure site before discharge. Patients are kept nil per mouth until after the
 213 fluoroscopy and are kept on a liquid diet for an additional 24 h. Patients are discharged
 214 with single dose PPI and a soft diet for 2 weeks.
 215

216
 217
 218

Figure 3 Schematic outline of the POEM procedure ¹¹

219 **8.3.1** *Risk of complications in POEM from recent clinical studies*

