220 So far there is limited information about the complications related to the POEM
221 procedure because it is a relative new procedure and long-term follow-up is not yet
222 available. Serious adverse events are not described in the previous studies that
223 performed POEM. The main preoperative complications that are described are
224 subcutaneous emphysema, pneumoperitoneum and pneumothorax. Transmural
225 openings into the mediastinum and into the peritoneal cavity caused emphysema,
226 pneumoperitoneum and pneumothorax. During POEM the inner circular muscle layer is
227 separated from the outer longitudinal muscle layer, leaving the longitudinal muscles
228 intact.⁹ The longitudinal muscle fibers are extremely thin, so minor damage can lead to
229 transmural dissections into the mediastinum and peritoneal cavity.

230 Subcutaneous emphysema was treated conservatively and in all cases the emphysema
231 resolved spontaneously in 2-3 days after surgery. The treatment of the
232 pneumoperitoneum occurred in all patients during the operation. A needle or canula of
233 18G was placed in the abdominal wall which gave directly relieve.^{8,9} A pneumothorax
234 was a rare complication and in all cases thoracic drainage was administered during the
235 operation which gave immediately relieve. Other described rare complications
236 preoperatively were a minor bleeding, controlled by endoscopic coagulation, and small
237 perforations which were clipped.

238 Postoperative complications were rare. One article described pneumothorax as an
239 important postoperatively complication.¹² The treatment was in most patients
240 conservatively and in some patients a thoracic drainage was administered, dependent
241 on the lung compression volume. An uncommon postoperative complication was a
242 delayed hemorrhage, one day after the operation. This occurred in one patient and was
243 probably caused by a bleeding in the submucosal tunnel. A three-cavity tube was placed
244 by endoscopy into the stomach and lower part of the esophagus to compress the
245 bleeding. After four days the tube was removed without further complications. Another
246 rare complication was a superficial ulcer (Forrest III) at the cardia that was detected with
247 a control endoscopy two days after POEM. This was only seen in one patient. The
248 patient had to continue PPIs and the hospital stay was extended. The control endoscopy
249 7 days after the procedure showed healing of the ulcer.

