387 All the additional measurements that are performed before and after treatment are safe
388 procedures and routinely performed in the clinical setting. Possible complications are
389 mainly due to placement of the catheters and endoscope. The catheters can give
390 discomfort in the nose and pharynx. Furthermore in rare cases a mucosal bleeding of
391 the nose, caused by the catheter, can occur which never need extra treatment. The
392 endoscope can give discomfort in the pharynx.

393

394 All adverse events reported spontaneously by the subject or observed by the
395 investigators will be recorded in a database. The Data Safety Monitoring Board will be
396 informed about the adverse events.

397

398 All serious adverse events (SAEs) will be reported through the web portal
399 *ToetsingOnline* to the accredited METC that approved the protocol. The SAEs will be
400 reported within 15 days after the sponsor is first notified of the SAEs.

401 The SAEs that result in death or are life treating will be reported expedited through the
402 web portal *ToetsingOnline* to the accredited METC that approved the protocol. This will
403 not occur later than 7 days after the coordinating investigators and principal investigator
404 have knowledge of the SAE(s). This first report is preliminary and within 8 days after
405 submission of the first report a final report will be submitted.

406

407 **9.3** *Follow-up of adverse events*

408 All adverse events will be followed until they have abated or until a stable situation has
409 been reached. Depending on the event, follow up may require additional tests or medical

410 procedures as indicated, and/or referral to another medical specialist. Furthermore a
411 Data Safety Monitoring Board will be informed about the adverse events that occur.

412

413 **9.4** *Data Safety Monitoring Board (see also the DSMB charter)*

414 A Data Safety Monitoring Board (DSMB) is established. In total the DSMB will consist of
415 four members, an epidemiologist, a surgeon, a paediatrician specialised in
416 gastroenterology and a gastroenterologist. None of the members have a conflict of
417 interest with the sponsor of the study. Personal details of the DSMB members can be
418 found in the DSMB charter which also describes in detail the function, aims and
419 responsibilities of the DSMB. In short the DSMB will act in an independent, expert and

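### PD patients have a scheduled 3-week contact and POEM patients have none from next-day discharge to 3 months: add one identical early complication checklist in both arms

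*Protocol*

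**What the plan says.** Section 8.1 (General follow up) asks PD patients for an "Eckardt score three weeks after the dilation" and, depending on the result, sends them to a second dilation or to manometry. The footnote to Table 1 limits the whole 3-week column: "only for patients randomised to balloon dilation". For both arms together, the first planned examination comes later: questionnaires are "filled in all patients 3 months after treatment and at 1, 2 and 5 years after treatment", with manometry and barium study on the same dates.

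Section 8.3 has patients come in two hours before the "POEM procedure and are discharged the next day". Before they leave there is one safety check: "On the next day postoperative fluoroscopy is performed to rule out a leak at the" closure site. Section 8.2 states no observation or imaging after a dilation.

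Section 9.2 gives the rule for recording: "All adverse events reported spontaneously by the subject or observed by the" investigators are entered in a database, and the DSMB is informed. No visit or call in either arm is given the task of asking about complications.

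Complications of any grade are a secondary outcome (section 6). Severe ones count against success in the primary outcome (section 5). The SAE incidence drives a stopping limit of 10%, with a review after every 20 inclusions (section 8.9, Premature termination of the study).

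**The concern.** When events are recorded only if a patient mentions them or an investigator sees them, the yield depends partly on how often, and how soon, patient and staff are in contact. Here that contact differs by arm by design. Section 8.1 brings PD patients back for manometry or a further dilation soon after week 3, while POEM patients have no planned contact for about three months after discharge.

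Two things are at stake. The first is the comparison of complications between arms: a mild event that has resolved by 3 months may be forgotten or never mentioned. The second is timeliness. Section 8.9 says the SAE incidence of POEM is not known, and a POEM patient treated shortly before a DSMB review may have had no planned contact since leaving hospital.

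**Working it through.** The plan gives no figure for ascertainment, so there is none to reproduce. The check sets the two schedules side by side and sizes the consequences by simple arithmetic.

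**Inputs.** Total enrolment 130 (section 11); allocation 1:1 (section 8.1); 62 patients per group in the power calculation (section 11); 3-week and 3-month time points (section 8.1, Table 1); DSMB review every 20 inclusions and SAE limit of 10% (section 8.9).

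**Scheduled contact by arm**

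| Time | PD | POEM |
|---|---|---|
| Day 1 | none stated | overnight stay, fluoroscopy for a leak |
| 3 weeks | Eckardt score, then manometry or second dilation | none |
| 3 months | common visit | common visit |

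- Patients per arm: 130 / 2 = 65.
- Time to first planned contact after the hospital stay: 3 weeks for PD and about 13 weeks for POEM. Ratio 13 / 3 = 4.3.
- This contrast shrinks for PD patients who have a second dilation. Section 8.2 places it within 6 weeks, and nothing is stated between it and the 3-month visit. If 3 months runs from the first dilation, a second one at week 6 leaves about 13 - 6 = 7 weeks without planned contact. If it runs from the second dilation, about 13 weeks.
- Section 8.1, section 8.2 and Table 1 give different Eckardt thresholds for the 3-week manometry and must be reconciled. The footnote confines the step to PD whichever is meant.

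**What the 3-week step collects.** It is a symptom score that decides on further dilation. No complication question is attached. Any advantage in ascertainment comes from staff being in touch with the patient, not from a stated enquiry.

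**DSMB.** Take the SAE limit as applying to each group. At the first review there are about 20 / 2 = 10 patients per arm. One SAE is 1 / 10 = 10%, at the limit; two are 2 / 10 = 20%, above it. So one event not yet known can decide whether the limit is passed. No recruitment rate is given, so the number of patients still inside their first three months at a review cannot be worked out.

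**Primary outcome.** A severe complication found late, but before 2 years, leaves the 2-year success proportion unchanged. Only one that is never found matters. Each such event, in a patient otherwise counted as a success, moves that arm's proportion by 1 / 62 = 1.6 percentage points. The documents give no basis for the number of such events.

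**The case against.** The strongest reply is that the 3-week step belongs to the PD treatment algorithm and is not a safety visit, so the protocol does not show that complications are sought better in PD. That stands, and it limits the point to opportunity for ascertainment.

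Several stronger readings are tempting but not supported:

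- *The schedule favours POEM.* PD has the extra contact at 3 weeks, but POEM has the extra observation and imaging on day 1, while the main complication of dilation named in section 9.2 is perforation. The two asymmetries may pull in opposite directions, and nothing in the protocol tells which is larger.
- *Early POEM complications are generally found late.* The admission and the leak check cover the immediate period, and severe events bring the patient back to care. The published events in section 8.3.1 do not prove otherwise. The haemorrhage came one day after the procedure, which is the planned discharge day. The ulcer was found by control endoscopy, which a call would not replace. Postoperative pneumothorax is called an "important postoperatively complication", but with no timing relative to discharge.
- *Capture is purely passive.* Section 9.2 also admits events that investigators observe. That does not remove the asymmetry, because investigators can observe only patients with whom they are in contact.
- *The primary comparison is biased.* Section 6 defines severe by longer admission, higher-level care, further endoscopy, transfusion or death. Such events leave records that can be collected at 3 months.
- *The DSMB is bound to learn too late.* Sections 9.2 to 9.4 have it informed of events apart from the 20-patient reviews.

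The CRF and the DSMB charter are mentioned but not shown, and either may already contain an early enquiry. None is stated in the protocol's own schedule.

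**Conclusion.** The point holds as a modest weakness in safety ascertainment that is cheap to repair; it is not an error in the primary comparison. Scheduled early contact differs by arm (3 weeks against about 13 weeks, for about 65 POEM patients), and no common enquiry is stated. Post-discharge complications, chiefly mild ones in a secondary outcome, may therefore be counted unequally, and some may come to the DSMB late.

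Neither the sign nor the size of any bias can be derived from the protocol. A percentage-point estimate would need detection rates that it does not give. The conclusion assumes that the CRF and charter add no early safety contact.

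**What to change.** Add one row to Table 1: a short structured complication and admission checklist, by telephone or post, at 3 weeks after the initial procedure in both arms, with the same questions at 3 months and at every later visit in both arms. Each checklist should cover the whole period since the last one, so that events after a second dilation are asked about at 3 months. Keep spontaneous reporting alongside it.

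Do not attach an Eckardt score, manometry or any treatment decision to the 3-week contact in POEM. The addendum (section 16) counts an Eckardt score above 3 within the first 2 years as failure, whereas section 8.2 treats a second dilation prompted by such a score at 3 weeks in PD as part of regular treatment. A 3-week Eckardt score in POEM would therefore create an occasion to fail the primary outcome in one arm only.

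The cost is about 65 short additional calls by existing staff, a brief CRF form, and slightly more mild events recorded.
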